2.1.3.3 Exploratory Endpoints

- The proportion of subjects with confirmed disability progression/improvement for at least 24 weeks

Confirmed disability progression was defined as an initial increase of ≥ 1.0 point from the baseline EDSS score (not attributable to another etiology, concurrent illness, or concomitant medication) when the baseline score was ≤ 5.5 , and of ≥ 0.5 point when the baseline score was > 5.5 , confirmed in a subsequent EDSS assessment 24 weeks later. Confirmed disability improvement followed the same criteria, but with a sustained decrease of ≥ 1.0 EDSS point from baseline.

- No evidence of disease activity (NEDA)

No evidence of disease activity (NEDA) was defined as no evidence of clinical (relapse, confirmed disability progression for 24 weeks) or MRI (T1-weighted gadolinium-enhancing or new/enlarging T2 lesions) disease activity.

2.1.4 Safety Variables

The safety analysis will be based on the reported DLTs, AEs and other safety information, such as clinical laboratory data, electrocardiogram (ECG), physical examination, and vital signs.

2.1.4.1 Adverse Events

Adverse events will be coded and classified according to the System Organ Class (SOC) and Preferred Term (PT) using the Medical Dictionary for Regulatory Activities (MedDRA).

The occurrence of AEs (including SAEs and adverse events of special interest [AESIs]) will be captured from the time the informed consent is obtained until the participant terminates participation in the study.

AESI will be categorized using a grouped set of MedDRA terms based on Standardized MedDRA Queries (SMQs) and clinical concept, as determined by the Sponsor. The MedDRA terms selected for AESI analysis will be provided in the Clinical Study Report (CSR).

Suicidal ideation and behavior will be identified by the AE preferred terms included in MedDRA SMQ “Suicide/self-injury”.

2.1.4.2 Laboratory Safety Variables

Clinical laboratory data consist of hematology, serum chemistry and coagulation. Clinical laboratory values will be analyzed after conversion into standard international units. International units will be used in all listings and tables.

The laboratory parameters will be classified as follows:

Hematology

Hematology and differential panel: hemoglobin, hematocrit, red blood cell count, mean corpuscular hemoglobin, white blood cell count, neutrophils, lymphocytes, monocytes, eosinophils, basophils, and platelets

Serum chemistry/ Pancreatic enzyme panel

The serum chemistry to be analyzed are presented in the table below.

Serum Chemistry		
Albumin	Creatinine	SGOT [AST]
Alkaline phosphatase	Glucose	SGPT [ALT]
Bicarbonate	LDH	Sodium
BUN	Magnesium	Total bilirubin
Calcium	Phosphorus	Total Protein
Chloride	Potassium	Uric acid

Coagulation

PT/INR and Fibrinogen

All observations of these tests including unscheduled measurements will be assigned to the appropriate safety analysis visit window, as defined in Section 2.5.3. In the presence of multiple measurements of the same laboratory test in the same window, the one closest to the targeted visit date will be used for the by-visit summaries. In case of equal distance, the later observation will be selected. All other lab results will only be listed.

2.1.4.3 Vital Signs

The following vital sign parameters will be analyzed:

- Systolic and diastolic blood pressures (mmHg)
- Heart Rate (beats/min)
- Weight (kg)
- Body Temperature (All results will be converted to Celsius)

2.1.4.4 Physical Examination

Physical examination is assessed per visit and body system, with possible outcomes normal and abnormal (plus free text for specification if abnormal).

2.1.4.5 ECG

ECG interpretation (normal/abnormal) and QTcF interval will be collected by visit and - where applicable - time point (pre-/post-dose).

2.1.5 Pharmacokinetic Variables

To characterize population PK of ublituximab, blood samples will be drawn from all subjects at pre-infusion and 15-30 minutes after the completion of the infusion on Day 1 and 15 and 180 (week 24); three additional sample will be taken at week 2, 4 and 25.

2.2 Analysis Populations

2.2.1 Safety Population

The Safety Population will include all subjects who receive at least one dose of Ublituximab. All safety assessments for Ublituximab including toxicity will be performed on the Safety Population.

The Placebo Safety Population will include all subjects who receive at least one dose of Placebo. All safety assessments for Placebo including toxicity will be performed on the Placebo Safety Population.

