## 5 TREATMENT PLAN

### 5.1 DOSING SCHEMA

**Table 6: Ublituximab/Placebo (Dose Range)**

Cohort	Randomization		Treatment Period	
	Subjects and treatment	Day 1/ infusion time	Day 15/ infusion time	Week 24/ infusion time
1	Placebo (n=2) b	Placebo / 4h	Placebo / 3h	-
	UTX (n=6)	150 mg / 4h	450 mg / 3h	450 mg / 1.5h
2	Placebo (n=2) b	Placebo / 4h	Placebo / 1.5h	-
	UTX (n=6)	150 mg / 4h	450 mg / 1.5h	450 mg / 1h
3	Placebo (n=2) b	Placebo / 4h	Placebo / 1h	-
	UTX (n=6)	150 mg / 4h	450 mg / 1h	600 mg / 1h
4	Placebo (n=2) b	Placebo / 3h	Placebo / 1h	-
	UTX (n=6)	150 mg / 3h	600 mg / 1h	600 mg / 1h
5	Placebo (n=2) b	Placebo / 2h	Placebo / 1h	-
	UTX (n=6)	150 mg / 2h	600 mg / 1h	600 mg / 1h
6	Placebo (n=2) b	Placebo / 1h	Placebo / 1h	-
	UTX (n=6)	150 mg / 1h	600 mg / 1h	600 mg / 1h
Cohort expansiona	Up to 100	To be explored at selected doses pending on the results of the above doses		

a Additional cohorts may be evaluated at doses ranging from 25 mg up to 900 mg to further elucidate the level of B-cell depletion and recovery parameters in subjects with RMS

b Following completion of Day 28, all placebo subjects will enter their respective “a” cohort and receive active treatment as described in Table 7 below. Further, the study evaluation table (section 7) will be restarted for these patients upon the initiation of active treatment with ublituximab

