## **5.2 AGENT ADMINISTRATION**

---

Treatment will be administered in the MS center. The MS centers must have skilled personnel and adequate equipment to provide emergency treatment should the subject experience anaphylaxis, hypotension or respiratory distress. Subjects will be enrolled into a specified cohort. A single dose of 150 mg of ublituximab on Day 1 with an infusion rate of 4 hours, 450 or 600 mg on Day 15 at different infusion rates (see dosing scheme), and at week 24, a single dose of 450 or 600 mg of ublituximab with different infusion rates will be administered to the respective cohorts. Additionally, 2 subjects in each cohort will be randomized to a placebo group. On day 28, the placebo subjects will begin active treatment with ublituximab in its respective cohort (see dosing scheme). Administration of ublituximab and placebo will be under the direction of the study investigators. Additional dosing cohorts may be explored.

It is required the absolute neutrophil counts and the platelet count should be within normal range before the infusion of ublituximab.

If the liver enzymes (ALT and/or AST) are > 5 times the upper limit of normal (ULN) of the normal range, or if the neutrophil count and platelets counts are below acceptable levels as described, the dose of ublituximab will be held for up to 48 hours until the laboratory values return to within acceptable range. If all labs above do not return to within the acceptable range within 48 hours, the subject will not receive the ublituximab infusion and will be withdrawn from the study. Subjects who are withdrawn will be asked to enter the follow-up evaluation period of the study.

---

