1.1 Study Design and Randomization

This is a 52-week, phase IIa, placebo-controlled, multi-center study that is primarily designed to assess the optimal dosing, optimal infusion time as well as safety/tolerability of ublituximab (TG1101; UTX) in patients with RMS.

Subjects may be screened up to 4 weeks before first dosing date. Qualified subjects will receive ublituximab on Days 1, 15, and week 24. There will be at least four treatment cohorts in the study with 8 subjects (2 placebo and 6 ublituximab treatment; please see treatment schema) enrolled in each cohort.

A Data and Safety Monitoring Board (DSMB) will be established to safeguard the wellbeing of the subjects and to advise the Sponsor whether it is appropriate to expand the enrollment to a dosing cohort or to initiate next dosing cohort. Once a subject is qualified, the Site will contact the Sponsor or its designee for cohort assignment (treatment assignment). The Sponsor or its designee will issue the cohort assignment for the subject using the following procedures. If DSMB deems that a cohort is not appropriate (e.g., due to safety), enrollment to that cohort and all higher cohorts will be terminated and all future subjects will be enrolled to the lowest incomplete cohort. Upon completion of first two patients in each cohort (one on placebo and one on study drug) through 21 days, the DSMB will review safety data and assuming no safety concern is raised, the remaining qualified subjects will be enrolled into such cohort.

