1.3 Determination of Sample Size

1.4 Study Plan

Refer to the study protocol for TG1101-RMS201 for study schedule for analysis variables.

- Ublituximab (IV): Infusions on Days 1 and 15 and week 24
- Placebo (IV): Infusions on Days 1 and 15

2 Statistical and Analytical Procedures

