2.4.5 Analyses of Safety Data

Safety results will be summarized and presented by cohort and total in safety population.

General common rules

All safety analyses will be performed on the Safety Population as defined in Section 2.2.1, unless otherwise specified, using the following common rules:

1. For quantitative safety parameters based on central laboratory/ reading measurements, visit and cohort will use descriptive statistics to summarize results and change from baseline values. Summaries will include the value and/or the worst value of the observation period.

2. All of the values including unscheduled measurements will be assigned to the appropriate safety analysis visit window. The safety analysis visit window is defined in Section 2.5.2. In the presence of multiple measurements of the same test in the same window, the one closest to the targeted visit date will be used for the by-visit summaries.
3. The analysis of the safety variables will in general be descriptive and no systematic statistical testing is planned.

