2.4.5.1 Analysis of Adverse Events

The Treatment-Emergent Adverse Events (TEAE) is defined as any AE that:

- Occurs after first dosing of study medication and through the end of the study or up through 30 days after the last dose of study treatment, or
- Is considered treatment-related regardless of the start date of the event, or
- Is present before first dosing of study medication but worsens in intensity or the investigator subsequently considers treatment related.

Dose-limiting toxicity (DLT) is defined in protocol section 5.1.1 and collected in eCRF.

Adverse event incidence tables will be presented by cohort and total, the number (n) and percentage (%) of subjects experiencing an AE. In a subset of tables, also all occurrences will be counted providing a severity of occurrence of the AE. The denominator for computation of percentages is the Safety Population within each cohort.

Not treatment emergent AE(s) summary:

- Listing of (not treatment emergent) AEs showing cohort, subject identifier, SOC, PT, verbatim term, date and day of onset, end date/time, duration, outcome, severity, date of death (if relevant), relationship to study treatment, action taken, AE seriousness and criteria.

TEAE(s) summaries:

The following TEAE summaries will be generated for the Safety Population.

Overview of TEAEs, summarizing number (%) of subjects with any

- (related/all) TEAE
- (related/all) Serious TEAE
- DLT
- (related/all) TEAE leading to death
- (related/all) TEAE of grade 3 or higher
- (related/all) TEAE leading to drug interruption
- (related/all) TEAE of special interest (AESI)
- (related/all) TEAE leading to permanent discontinuation

- TEAEs by primary SOC and PT, showing number (%) of subjects with at least one TEAE, sorted alphabetically by SOC and decreasing incidence of PTs within SOC for the total column. This sorting order will be applied to all other tables, unless otherwise specified.
- TEAEs by PT, sorted by decreasing frequency in the total column.
- All at least possibly drug related TEAEs by primary SOC and PT, showing number (%) of subjects with at least one possibly related TEAE, sorted by sorting order defined above.
- All TEAEs by maximal severity, presented by primary SOC and PT, showing number (%) of subjects with at least one TEAE by severity (ie, mild, moderate, or severe), sorted by sorting order defined above.

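### The SAP specifies no adverse-event table comparing the randomised arms over Days 1-28, the only period with concurrent placebo control, and sets no end to the placebo observation period

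*SAP*

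**What the plan says.** Each cohort is planned as "8 subjects (2 placebo and 6 ublituximab treatment" (SAP 1.1), and Protocol 5.2 confirms that "2 subjects in each cohort will be randomized to a placebo group". Placebo subjects have two infusions: "Placebo (IV): Infusions on Days 1 and 15" (SAP 1.4). The footnote to Protocol Table 6 then moves them to active drug: "Following completion of Day 28, all placebo subjects will enter their respective" active-treatment cohort. Their evaluation schedule "will be restarted for these patients upon the initiation of active treatment with ublituximab".

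SAP 2.2.1 defines two safety sets. The Safety Population is everyone ever given ublituximab, which includes placebo starters once they have crossed over. A separate Placebo Safety Population covers everyone ever given placebo, and "All safety assessments for Placebo including toxicity will be performed on the Placebo Safety Population".

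SAP 2.4.5 then states: "Safety results will be summarized and presented by cohort and total in safety population". SAP 2.4.5.1 gives AE incidence as the percentage of Safety Population subjects in each cohort. A treatment-emergent event is one that starts after first dosing and "through the end of the study or up through 30 days after the last dose of study treatment". Follow-up-adjusted rates are mentioned once, as an option for suicidal ideation and behaviour.

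**The concern.** Days 1-28 are the only time when subjects allocated at random to ublituximab or placebo are observed concurrently, with the same infusion days and cohort-matched infusion times. Only in that window can effects of the drug be separated from those of the infusion procedure, the premedication and the disease. The planned AE tables do not isolate it. On one side are up to 48 weeks of ublituximab, with placebo starters counted after crossover. On the other is a short placebo period whose end is not defined. Subject percentages grow with observation time, so anyone who sets the two side by side may see an excess on ublituximab that follow-up alone explains. The placebo arm would then add little to the safety account of a trial that carries placebo control in its title and names safety and tolerability among its main design aims.

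**Working it through.** The plan gives no AE rate, and the public text shows only headings for sample size (Protocol 9.1, SAP 1.3), so there is no stated figure to reproduce. The AE risks below are assumptions, shown as ranges.

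**1. Is there a day-matched table by arm?** The AE summaries in SAP 2.4.5.1 are specified for the Safety Population, by cohort, over the full treatment-emergent window. Three kinds of output do touch the first four weeks:
- *Dose-limiting toxicity table.* It is restricted to the first 4 weeks of treatment, but an event must be at least possibly related to ublituximab (Protocol 5.1.1). No placebo column is specified.
- *Laboratory, vital-sign and ECG summaries by visit.* Day 1 to Week 4 appear as separate visits. However, SAP 2.1 ties baseline to the first ublituximab dose, and the Week 3 window in SAP 2.5.3 is anchored to the second ublituximab administration. For placebo starters in the Safety Population, these visits therefore describe time after crossover.
- *AE listings.* They give the day of onset but are not a summary by arm.

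**2. When does placebo observation end?** No cut-off is stated. Read literally, the 30-day limb runs from the second placebo infusion: Day 15 + 30 = Day 45, which is 45 - 28 = 17 days past crossover. The end-of-study limb runs further. One event could then count in both populations.

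**3. Exposure ratio.**
- Ublituximab to Week 48 against placebo to Day 28: 336 / 28 = 12.
- Ublituximab to 30 days after the Week 24 dose: (168 + 30) / 28 = 198 / 28, about 7.1.

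Both take placebo time as 28 days, which is inferred from the crossover and not stated in the SAP.

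**4. Equal constant hazard, no drug effect.** Risk over D days = 1 - (1 - p)^(D/28), where p is the assumed 28-day risk. For p = 10%: 1 - 0.9^12 = 0.718 and 1 - 0.9^7.07 = 0.525.

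| 28-day risk, both arms | Ublituximab, 336 days | Ublituximab, 198 days |
|---|---|---|
| 5% | 46% | 30% |
| 10% | 72% | 53% |
| 20% | 93% | 79% |
| 30% | 99% | 92% |

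**5. Events only at infusions, no drug effect.** Risk = 1 - (1 - q)^k, with k = 2 placebo or 3 ublituximab infusions. For an assumed q = 20%: 1 - 0.8^2 = 36% and 1 - 0.8^3 = 49%. At q = 10% the figures are 19% and 27%.

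**6. What a matched table would hold.**
- Six full cohorts: 6 x 6 = 36 ublituximab and 6 x 2 = 12 placebo. Four cohorts: 24 and 8.
- Precision: with 0/12 placebo events, the exact 95% upper limit is 1 - 0.025^(1/12) = 26%.

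**The case against.** The strongest reply is that the plan never proposes the misleading comparison. The two populations are kept apart, safety analysis is described as generally descriptive without systematic testing, the safety objective concerns ublituximab alone, and Protocol 9.8 says the study is not powered for treatment differences. This stands to a degree: the bias arises only if someone reads the percentages together. It argues against formal tests, but not against a descriptive table on equal days.

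Several stronger readings are tempting, and the documents do not support them:
- *No safety output covers the early days.* The dose-limiting toxicity table and the by-visit summaries do. What is missing is an AE table with the arms side by side.
- *Placebo AEs are reported over exactly 28 days.* The SAP sets no such limit; the period is undefined.
- *The randomised comparison can never be made.* It is only not planned in the SAP. The data are collected, Protocol 9.8 leaves treatment differences optional for efficacy, and Protocol 10.7.2 summarises laboratory toxicity by treatment group.
- *AE incidence is biased by a factor of 12.* Twelve is an exposure ratio, and the largest distortion needs a constant hazard over 48 weeks. Protocol 8.1.1 lists infusion reactions, pyrexia and chills among the common related events. If such events cluster at infusions, the distortion is much smaller.
- *The comparison would be 36 v 12.* Only four cohorts are assured as a minimum, and the safety board may advise closing one.

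It is also fair to say that the visible text describes no blinding, so even a day-matched AE table could carry reporting differences between arms.

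**Conclusion.** The point holds for adverse events: the SAP plans no Day 1-28 AE table by randomised arm and leaves the end of placebo observation open. The size of any false difference depends on how events are spread over time. With equal true risk and 28 days of placebo time, it ranges from 36% v 49% (events only at infusions, 20% each) to 10% v 53% or 72% (constant hazard, with 198 or 336 days of ublituximab follow-up). These figures illustrate the range and do not predict the trial's results. The gap does not invalidate the 48-week ublituximab tables as a description of treated subjects. It means that the planned AE tables provide no randomised safety contrast, although the data for one exist. It should be corrected, and the cost is low.

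**What to change.** 1. State that the placebo period ends just before the first ublituximab dose, so that no event counts in both populations.
2. Add one descriptive table set by randomised arm, pooled over cohorts, from the first study infusion to Day 28, or to the first ublituximab dose for placebo starters if that is earlier. Placebo starters appear in the placebo column only. Pooling does not confound arm with cohort while every cohort keeps its 3:1 ratio.
3. Include any AE, Grade 3 or higher, serious, and infusion-associated events (onset in or within 24 hours of an infusion, a safety endpoint in the protocol synopsis), plus laboratory changes. For this table set, take baseline before the first study infusion; under the current definition, change during the placebo period cannot be computed properly.
4. Risk differences with exact 95% confidence intervals may be shown descriptively.
5. Label the 48-week tables as ublituximab-only.

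The cost is a few extra tables and one additional baseline derivation, with no new data collection. The drawback is wide intervals with 12 or fewer placebo subjects, which the table should acknowledge.

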2.2.2 Intent-to-Treat (ITT)

The Intent-to-Treat (ITT) population will consist of all subjects who receive at least one dose of Ublituximab. The primary efficacy analyses will be performed based on the ITT population.

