### **5.2.1 GUIDELINES FOR ADMINISTRATION OF UBLITUXIMAB**

---

- *Necessity of MS Center:* Center must have personnel and equipment necessary to provide adequate emergency treatment for anaphylaxis, hypotension and respiratory distress.
- *Method of Administration:* Ublituximab must be administered as an intravenous infusion through a dedicated intravenous line and will be done under the supervision of the study investigator
- *Potential Drug Interactions:* No drug interactions have been reported to date.
- *Pre-medications:* Pre-medicate approximately 30 minutes prior to each dose of ublituximab with an antihistamine (diphenhydramine 50 mg or equivalent), and corticosteroid (dexamethasone 10-20mg or equivalent). Oral acetaminophen, 650 mg (or equivalent; only used for intervention) should be restricted to patient who experience fever or pyrexia after week 1 dose, or as clinically warranted and additional medication (which needs to be documented) may be used at discretion of the physician if adverse reactions occur.

- *Hypersensitivity and Infusion Reaction Precautions:* Medication and resuscitation equipment utilized by a trained personnel must be available per institutional guidelines prior to ublituximab administration for the emergency management of potential anaphylactic reactions
- *Subject Care Implications:*
  - Ublituximab should not be administered as an IV push or bolus.
  - Ublituximab should only be diluted in 0.9% NaCl.
  - Diluted ublituximab should be checked before administration for cloudiness, color, or deposits. Ublituximab should not be administered if it does not conform to the manufacturer's specifications. The Monitor/Sponsor must be informed immediately of any quality concerns or questions about the product.
  - It is recommended that ublituximab be administered immediately after dilution.
  - No other treatment may be co-administered with ublituximab (other than for immediate intervention for adverse event).

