### 6.2.1.2 INFUSION RELATED REACTIONS

Infusion related reactions have been reported with ublituximab. All subjects treated with ublituximab require pre-medication approximately 30 minutes prior to each dose of ublituximab or placebo with an antihistamine (diphenhydramine 50 mg or equivalent), and a corticosteroid (dexamethasone 10-20 mg or equivalent). Symptomatic infusion reactions, despite premedication, may be treated at the discretion of the treating physician, including but not limited to: oral acetaminophen 650 mg (or equivalent), corticosteroids, antihistamines, oxygen and bronchodilators.

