### 7.1.2 RADIOLOGICAL EVALUATION

Assessment of effect on Gd enhancing lesion and new and enlarging T2 lesions will be evaluated as outlined in the schedule of events. For subjects initially treated with placebo, they will obtain a MRI at baseline and on week 4 (prior to start of UTX treatment).

Additionally, all study MRIs will undergo safety review by the site radiologist to identify any new clinical relevant abnormal MRI findings that are not consistent with the diagnosis of MS, with particular attention to the possibility of progressive multifocal leukoencephalopathy, and provide a report of the MRI to the treating physician.

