### 9.3 ANALYSIS POPULATIONS

---

The Intent-to-Treat (ITT) population will consist of all subjects who receive at least one dose of study drug and provide some efficacy values. The primary efficacy analyses will be performed based on the ITT population.

The Safety Population will include all subjects who receive at least one dose of study drug. All safety assessments including toxicity will be performed on the Safety Population.

The modified intent-to-treat Population (mITT) will consist of all subjects who have received UTX and have one baseline and post-baseline MRI without a major protocol deviation. The criteria for a major protocol deviation will be determined and documented prior to data base lock. Subject exclusion from the mITT population will also be determined and documented prior to database lock. Supportive analyses may be performed based on the mITT population.

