2.1 Analysis Variables

Baseline for both efficacy and safety variables are defined as the last non-missing value on or before the first dose of Ublituximab.

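### The SAP ties ITT and baseline to the first ublituximab dose, so B-cell data collected on placebo are not used as a concurrent control for the primary endpoint

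*SAP*

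**What the plan says.** - **Population.** SAP 2.2.2: "The Intent-to-Treat (ITT) population will consist of all subjects who receive at least one dose of Ublituximab". The primary efficacy analysis uses this set. Protocol 9.3 defines ITT as "all subjects who receive at least one dose of study drug and provide some efficacy values".
- **Baseline.** SAP 2.1: "Baseline for both efficacy and safety variables are defined as the last non-missing value on or before the first dose of Ublituximab".
- **Primary endpoint.** SAP 2.1.3.1 and 2.4.2 time the Week 4 responder rate from the second ublituximab infusion and report it per cohort and overall, with exact intervals if appropriate. No placebo group is named. The only modelling mentioned is an optional dose-response trend test.
- **Placebo period.** Protocol Table 1 allocates 2 placebo and 6 ublituximab subjects per cohort. After Day 28, placebo subjects move to the matching 'a' cohort and restart the evaluation schedule. The synopsis laboratory schedule has immune profiling during the placebo period at screening, baseline, Days 1, 2, 8 and 15, and Week 4, then again from a new pre-dose Day 1 on ublituximab.
- **Placebo in other SAP outputs.** Placebo appears in disposition, in the count of placebo infusions (SAP 2.1.2) and in a separate Placebo Safety Population (SAP 2.2.1).
- **MRI.** Protocol 7.1.2 gives initially-placebo subjects an MRI at baseline and another at Week 4, before ublituximab starts. The Section 7 table schedules MRI only at screening, Week 24 and Week 48.
- **Premedication.** Protocol 6.2.1.2 requires it "prior to each dose of ublituximab or placebo with an antihistamine" and a corticosteroid. Protocol 5.2.1 says "Pre-medicate approximately 30 minutes prior to each dose of ublituximab with an antihistamine", and 5.3 likewise mentions ublituximab only.

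**The concern.** The trial is titled placebo-controlled, and its randomised placebo period runs to Day 28. SAP 2.5.3 gives Week 4 a target of Day 28, so the control period covers the primary endpoint window. Yet ITT, baseline and Week 4 are all defined relative to ublituximab, and no efficacy output shows what happened to B cells on placebo. The primary result is then a before-after description on active drug alone, and the reader cannot see how far CD19+ counts move over four weeks without ublituximab, although those counts were collected.

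The baseline rule reaches further than efficacy. It also covers safety variables, so it governs any change-from-baseline summary in the Placebo Safety Population.

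**Working it through.** The public text shows only headings for sample size (Protocol 9.1, SAP 1.3), so there is no stated figure to reproduce.

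**1. Trace one placebo subject.** Let *a* be the CD19+ value before the first placebo infusion, *b* the Week 4 value on placebo, *c* the last value on or before the first ublituximab dose, and *d* the Week 4 value after the restart on ublituximab.
- Reduction under SAP 2.1 and 2.4.2: 100 × (c − d)/c.
- Reduction on placebo: 100 × (a − b)/a. No SAP section defines or displays this.
- For a subject randomised to ublituximab, *a* and *c* are the same value, so the rule does no harm there.
- A placebo subject who never receives ublituximab is not in the SAP's ITT.

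Efficacy is summarised by nominal visit (SAP 2.5.2), and a placebo subject has two sets of early visits with the same labels. The SAP does not say how the by-visit B-cell summary keeps them apart, or whether cohort rows merge the 'a' cohorts with the original ublituximab subjects.

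**2. Apply the same rule to placebo safety.** The reference is the "last non-missing value on or before the first dose of Ublituximab". For a placebo subject that falls at the end of the placebo period, after the observations it is meant to precede. A subject who never receives ublituximab has no defined reference date.

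**3. Count the subjects**, assuming cohorts fill and all placebo subjects cross over.

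| Cohorts | Placebo (2 each) | Randomised ublituximab (6 each) | SAP ITT | Initially placebo | Shown as placebo |
|---|---|---|---|---|---|
| 4 | 8 | 24 | 32 | 8/32 = 25% | 0 |
| 6 | 12 | 36 | 48 | 12/48 = 25% | 0 |

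**4. Precision of a placebo column.** With 0 responders of n, the exact (Clopper-Pearson) 95% upper limit is 1 − 0.025^(1/n):
- n = 2 (one cohort): 1 − 0.025^(1/2) = 84.2%
- n = 8 (four cohorts): 1 − 0.025^(1/8) = 36.9%
- n = 12 (six cohorts): 1 − 0.025^(1/12) = 26.5%

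If all n respond, the lower limit is 0.025^(1/n): 54.1% for n = 6 and 90.3% for n = 36. The documents give no expected responder rates, so these results are illustrations. They show that placebo is uninformative within a cohort and useful only when pooled. Allocation is 6:2 in every tabulated cohort, so pooling full cohorts does not confound arm with cohort.

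**5. MRI.** Only initially-placebo subjects have a Week 4 scan. A change from original baseline to Week 4 can be calculated for them, but there is no ublituximab Week 4 scan to set against it.

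**The case against.** The strongest case against is that nothing planned has been removed. Protocol 9.8 says the study is not powered for treatment differences and makes their analysis optional. Protocol 9.8.1 names no placebo comparison for the primary variable. The primary objectives concern depletion by ublituximab, and the optimal dose and infusion time. Placebo subjects still contribute after crossover, and placebo safety has its own population. All of this stands. It rules out any claim that a powered test is missing, and it limits the weight of the point. It does not explain why randomised control data covering the primary window should go unreported.

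Four stronger readings are tempting, and the documents do not support them:
- **The placebo Week 4 MRI is discarded.** Under SAP 2.1 that scan can become the subject's analysis baseline, and SAP 2.4.3 summarises baseline scans. What is not reported is the change while on placebo. Likewise, the last pre-ublituximab B-cell value serves as baseline.
- **The SAP plainly contradicts the protocol by dropping placebo from ITT.** *Study drug* in Protocol 9.3 is ambiguous. The synopsis contrasts it with placebo, while the mITT definition in 9.3 uses UTX, which suggests that ITT was meant to be wider. The clearer difference is that the SAP omits the protocol's requirement for some efficacy values.
- **Corticosteroid premedication biases the responder rate.** The documents give no figure for such an effect, and they disagree on whether placebo subjects are premedicated.
- **A comparison would be overwhelmingly significant.** Setting 36/36 against 0/12 gives a tiny p-value only because the extreme result was chosen.

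**Conclusion.** The point holds as a gap in the analysis plan; the design itself does collect the control data. As written, the SAP gives no placebo-period summary of B-cell change or Week 4 response, so the primary endpoint is reported without a concurrent control. Its single baseline rule, taken literally, also misplaces the reference for change-from-baseline summaries on placebo.

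In size, this affects up to 12 randomised placebo subjects (8 with four cohorts), a quarter of ITT if cohorts fill and all cross over. No bias in the ublituximab responder rate can be calculated from the documents, and none is claimed. What is lost is context for a descriptive result. The change should be made because it is cheap and lets the trial use its own control, but the study remains unpowered for comparison.

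**What to change.** 1. **SAP 2.1:** for the placebo period, define baseline as the last value before the first study infusion, placebo or ublituximab. Use it for placebo-period efficacy and for the Placebo Safety Population. Keep the present rule for analyses of the ublituximab period.
2. **SAP 2.2:** define a Day 1 to 28 randomised set. Count placebo subjects in it whether or not they later receive ublituximab, and use only their values from before the first ublituximab infusion.
3. **SAP 2.4.2:** add a descriptive pooled-placebo column beside the subjects randomised to ublituximab, for B-cell change by visit and Week 4 response with exact 95% CIs. Keep 'a' cohort subjects out of the randomised ublituximab column, and state whether the existing cohort rows include them.
4. **MRI:** list the placebo change from original baseline to Week 4 descriptively, without a between-arm comparison.
5. **Wording:** state whether *study drug* in the Protocol 9.3 ITT definition includes placebo, and align the protocol and SAP definitions, including the efficacy-values condition. Reconcile Protocol 6.2.1.2 with 5.2.1 and 5.3 on premedication before placebo.

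The cost is a few extra tables from data already scheduled for collection. The placebo group is small and its intervals will be wide, and the text should say that no powered comparison is implied.
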